9.5.3 Unsolicited AEs

All the unsolicited AEs occurring during the study will be recorded, regardless of their assessment of relatedness by the Investigator.

The original verbatim terms used by Investigators to identify AEs will be mapped to preferred terms using the MedDRA dictionary. The unsolicited AEs will then be grouped by MedDRA preferred terms into frequency tables according to system organ class (SOC). All reported AEs, as well as AEs judged by the Investigator as at least possibly related to study vaccine, will be summarized by treatment group, according to SOC and preferred term within SOC. When an unsolicited AE occurs more than once for a subject, the maximum severity reported and strongest reported relationship to the treatment group will be counted.

Only TEAEs will be summarized as defined in [Section 7.1.1](#). The selection of unsolicited AEs and their assignment to time intervals will be done by day of onset and not by days ongoing/persisting.

Unsolicited AEs will be summarized by alphabetic SOC, and preferred term as follows:

- Any unsolicited TEAE
- Possibly or probably related unsolicited TEAEs
- SAEs
- Possibly or probably related SAE
- Unsolicited TEAE leading to withdrawal
- Any AE leading to death

Listings of all TEAEs will be provided by subject.

9.5.4 Combined Solicited and Unsolicited AEs

Solicited AEs continuing beyond 7 days after any injection will be coded by MedDRA and combined with the unsolicited AEs. An overall summary of subjects with all combined solicited and unsolicited AEs, by SOC and preferred term, will be provided as well.

9.5.5 Analysis of Other Safety Data

The frequencies and percentages of concomitant medications will be tabulated by treatment group. Medications will be coded using the WHODRUG dictionary.

9.6 Immunogenicity Analysis

9.6.1 GMT/GMR

Immunogenicity analyses will be performed for both OPA (titers) and IgG (mcg/mL). All immunogenicity analyses will be based on the IEP and Exposed Population.

The GMTs and GMCs will be analyzed via linear models. The primary model is an analysis of variance (ANOVA), with logarithmically transformed titers (\log_{10}) as the dependent variable and treatment group and study site as the fixed effects in the model. The results included in the main tables of this report will be based on this basic ANOVA model. As a secondary analysis, to remove the effect of baseline concentration on the GMTs, an analysis of covariance (ANCOVA) will also be performed. The ANCOVA includes treatment group and study site as the fixed effects and \log_{10} baseline titer as the covariate in the model. The rationale for including baseline values as a covariate is that prior data have shown vaccine response is correlated with baseline antibody levels.

The least squares means and their 95% confidence intervals (CIs) calculated based on the ANOVA and ANCOVA will be back transformed and reported as the group GMT and GMC values (adjusted for the mean baseline in the case of the ANCOVA). GMRs will also be calculated from the ANCOVA and ANOVA models.

Comparisons between relevant groups will be based on the estimated adjusted GMTs measured at Day 29 for 24 serotypes in VAX-24 (of those 20 in PCV20), and mean square error calculated from the basic ANOVA model using contrast statements. The analysis of GMFR relative to Day 1 will also be computed using similar models.

The main comparison of interest will be the three VAX-24 dose levels group versus the PCV20 (20 serotypes) group. However, the three VAX-24 dose groups will also be compared in a pairwise fashion on a serotype-by-serotype basis. No adjustment for multiplicity will be applied and missing data will not be imputed.

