4. ANALYSIS SETS

4.1. Analysis Set Definitions

The following Analysis sets will be evaluated and used for presentation and analysis of the data:

- **Screened Population:** Includes all screened subjects who provided informed consent and were assigned a study subject number, regardless of whether the subject was randomized or not. This population will be used to account fully for subject disposition, starting with the informed consent. The screened population will not be analyzed as such but will be available in the clinical database.
- **Randomized Population:** Includes all subjects from the Screened Population who consented, provided demographic and other Baseline Screening measurements, and were randomized. Each subject will be analyzed as randomized.
- **Exposed Population:** Includes all subjects from the Screened Population who received at least one study vaccine administration. Each subject will be analyzed as treated.
- **Safety Population :** Includes all subjects in the Exposed Population but excluding subjects lost to follow up at Day 1 reporting no solicited or unsolicited AEs. Each subject will be analyzed as treated.
- **Immunogenicity Evaluable Population (IEP):** Includes all subjects in the Exposed Population who:
 - Had no major protocol deviation that would impact immunogenicity assessment or other reason to be excluded as defined prior to unblinding or analysis.
 - Had not received a prohibited medication or vaccine. Identification of subjects receiving prohibited medications will be done via a medical review from the Sponsor of a listing of all concomitant medications.
 - Provided evaluable serum sample results for baseline, the relevant post-vaccination time points, and within the required time frames:
 - Baseline: Day 1 or within 30 days before first study vaccine administration
 - Day 29: Day 26 through Day 34, inclusive

Each subject will be analyzed as treated. Programming identification of patients excluded of the IEP is detailed in Section 4.2.

“As randomized” means according to the vaccine regimen to which the subject was randomized, while “as treated” means according to the vaccine regimen a subject received, rather than the vaccine regimen to which the subject may have been randomized.

The Randomized Population will be used for the analysis of exposure.

The Safety Population will be the primary set for the analysis of the safety parameters.

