 - **GMR:** The geometric mean ratio = antilog (LSMeans [log₁₀ x]) / antilog(LSMeans [log₁₀ y]), where x and y are the 2 assays results and LSMeans is the least square means calculated by the model.
 - **Fold Ratio:** The ratio between titer/concentration at Day 29 visit and the one at Day 1.
 - **GMFR:** The geometric mean fold ratio = antilog (LSMeans [log₁₀ y]), where y is the assay fold ratio and LSMeans is the least square means calculated by the model.
 - **4-fold increase:** A subject achieved 4-fold increase if fold ratio ≥ 4
 - **BLQ:** Below lower limit of quantification (LLOQ). Per Center for Biologics Evaluation and Research (CBER) criterion, BLQ titer/concentration will be analyzed as:
 - 0.5*LLOQ for calculations of GMT/GMC and GMT/GMC Ratios (GMRs)
 - 1*LLOQ for calculations of fold ratio.
 - **ULOQ:** Upper limit of quantification. Titer/Concentration above ULOQ will be analyzed as:
 - 1*ULOQ for all calculations (GMT/GMC, GMRs, fold-ratio)

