6.1.3. Adjustments for Covariates

The randomization in this study will not be stratified.

The following variables will be used for adjustment in immunogenicity analyses:

- For the Analysis of variance (ANOVA), study site will be included as fixed effect in the model.
- For the Analysis of covariance (ANCOVA) and the logistic regression, study site will be included as fixed effect and the log baseline titer will be included as covariate in the model. In case the model does not converge, the log₁₀ baseline titer will be removed from the model and a footnote explicating the change will be added.

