6.5.1. GMT/GMC, GMR and GMFR

To estimate the immunogenicity response 1 month first vaccination, OPA titers (log₁₀) and IgG concentrations (mcg/mL) measured at Day 29 visit will be logarithmically transformed for analysis and GMTs/GMCs will be computed with 95% CI for each assay using ANOVA and ANCOVA.

- First model in an ANOVA with log₁₀-transformed concentrations/titers at Day 29 as the dependent variable and treatment group and study site as the fixed effects in the model.
- Second model in an ANCOVA with log₁₀-transformed concentrations/titers at Day 29 as the dependent variable, treatment group and study site as the fixed effects and log₁₀ baseline concentration/titer as the covariate.

The least squares means, and their 95% CIs calculated based on the ANOVA and ANCOVA will be back transformed and reported as the group GMT and GMC values. Comparisons between relevant groups will be based on the estimated adjusted GMTs measured at Day 29 visit for 24 serotypes in VAX-24 (of those 20 in PCV20), and mean square error calculated from the basic ANOVA model using contrast statements. The main comparison of interest will be the three VAX-24 dose levels group versus the PCV20 (20 serotypes) group. However, the three VAX-24 dose groups will also be compared in a pairwise fashion on a serotype-by-serotype basis. No adjustment for multiplicity will be applied and missing data will not be imputed. GMRs will also be calculated from the ANCOVA and ANOVA models.

The analysis of GMFR at Day 29 relative to Day 1 will also be computed using similar models:

- First model in an ANOVA with log₁₀-transformed fold ratio at Day 29 as dependent variable and treatment group and study site as the fixed effects in the model.
- Second model in an ANCOVA with log₁₀-transformed fold ratio at Day 29 as dependent variable, treatment group and study site as the fixed effects and log₁₀ baseline concentration/titer as the covariate.

The least squares means, and their 95% CIs calculated based on the ANOVA and ANCOVA will be back transformed and reported as the group GMFR value.

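### The lead GMT, GMC and GMR model leaves out baseline titer although the protocol says response depends on it; the planned ANCOVA should lead, and the contrast sentence should name one model

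*Protocol*

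**What the plan says.** Protocol 9.6.1 makes an ANOVA on log10 Day 29 titer the primary model, with treatment group and study site as fixed effects, and adds: "The results included in the main tables of this report will be based on this basic ANOVA model". An ANCOVA that also contains log10 baseline titer is secondary. Its stated rationale is that "prior data have shown vaccine response is correlated with baseline antibody levels".

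SAP 6.5.1 lists the same two models as first and second and reports least squares means, intervals and GMRs from both. SAP 6.5.2 draws the GMT and GMC bar plots and the GMR and GMFR forest plots from the ANOVA.

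On contrasts, SAP 6.5.1 repeats the protocol: "Comparisons between relevant groups will be based on the estimated adjusted GMTs measured at Day 29 visit". The same sentence then takes the mean square error from the ANOVA.

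Baseline data are available. Day 1 serum is drawn from every subject, and SAP 4.1 admits to the IEP, the primary immunogenicity set, only subjects who "Provided evaluable serum sample results for baseline, the relevant post-vaccination time points, and within the required time frames". Baseline titer already enters one model directly. For the 4-fold rise in the four serotypes not in PCV20, SAP 6.1.3 says that in "the logistic regression, study site will be included as fixed effect and the log baseline titer will be included as covariate".

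**The concern.** The protocol names a predictor of the outcome, measures it in everyone, and then leads with the model that omits it. The comparison of each VAX-24 dose with PCV20 on the 20 shared serotypes is the one the plan singles out. With about 50 subjects per arm, its lead GMRs would have wider intervals than the data allow. Each serotype's GMR would also carry whatever baseline difference randomization happened to leave. In a dose-finding study meant to inform later trials, that precision is worth having.

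The contrast sentence is a second, separate problem. The word adjusted could mean adjusted for site, since SAP 6.1.3 lists site under covariate adjustment: "For the Analysis of variance (ANOVA), study site will be included as fixed effect in the model". It could also mean adjusted for baseline, because the parenthesis in Protocol 9.6.1 on group GMTs ties adjustment to the mean baseline under the ANCOVA. On the second reading the estimate comes from one model and its error from another. Two programmers could therefore report different intervals for the same comparison.

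**Working it through.** **Inputs from the documents.** 200 subjects allocated 1:1:1:1 (SAP 2.3), so 200/4 = 50 per arm. About 20 sites (Protocol synopsis), with site as a fixed effect. Two-sided 0.05, so 95% intervals. Error degrees of freedom are 200 − 4 − 19 = 177 for the ANOVA and 176 for the ANCOVA. The plan states no power, SD, effect size or correlation, so there is no plan figure to reproduce beyond the 50 per arm.

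**Assumed.** Log10 SD 0.6, the same at baseline and Day 29, and baseline-to-Day-29 correlation r from 0 to 0.7.

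**Step 1: formula.** For one dose versus PCV20, the ANOVA half-width is t × SD × √(2/50) = 1.973 × 0.6 × 0.2 = 0.237 on the log10 scale, which is a GMR multiplier of 10^0.237 = 1.73. The ANCOVA multiplies the half-width by about √(1 − r²).

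**Step 2: simulation.** Four arms of 50, subjects assigned at random to 20 sites, 3000 trials per r. The ANOVA multiplier is 1.77. It exceeds 1.73 because sites are not exactly balanced over arms.

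| r | √(1 − r²) | simulated width ratio, ANCOVA/ANOVA | ANCOVA GMR multiplier |
|---|---|---|---|
| 0 | 1.000 | 1.003 | – |
| 0.1 | 0.995 | 0.998 | – |
| 0.2 | 0.980 | 0.982 | 1.76 |
| 0.3 | 0.954 | 0.957 | 1.73 |
| 0.5 | 0.866 | 0.869 | 1.65 |
| 0.7 | 0.714 | 0.717 | 1.51 |

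Coverage was 0.951 to 0.954 for the ANOVA and 0.947 to 0.954 for the ANCOVA. In a separate simulation with subjects spread evenly over sites, the mean log10 error of either model was no more than about 0.002, so neither is biased. With the degrees of freedom taken into account, the formula ratios at r = 0.3, 0.5 and 0.7 are 0.959, 0.871 and 0.718. The effective sample size per arm, 50/ratio², is then about 54, 66 and 97.

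**Step 3: baselines below the LLOQ.** SAP 5.2 sets such values to half the LLOQ for GMTs and GMRs. Applying that rule to the baseline covariate (1500 trials per cell, r before censoring, Day 29 uncensored) gives these width ratios:

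| Baselines below LLOQ | r = 0.3 | r = 0.5 | r = 0.7 |
|---|---|---|---|
| 30% | 0.960 | 0.879 | 0.742 |
| 50% | 0.966 | 0.896 | 0.778 |
| 70% | 0.974 | 0.918 | 0.830 |

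**Step 4: chance imbalance.** A baseline difference of one standard error moves the unadjusted GMR by a factor of 10^(SD × √(2/50) × r). At SD 0.6 and r = 0.5 this is 10^0.06 = 1.15. It runs from 1.05 (SD 0.5, r = 0.2) to 1.25 (SD 0.7, r = 0.7). The ANOVA interval already allows for this movement, so it is the same imprecision seen in a single trial and not an additional harm.

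**Step 5: the mixed reading of the contrast sentence.** Using the ANCOVA estimate with the ANOVA mean square error gave simulated coverage of 95.9%, 97.2% and 99.5% at r = 0.3, 0.5 and 0.7, against a nominal 95%. Those intervals are too wide.

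**The case against.** The strongest reply is that this is a choice between two valid, pre-specified models. Immunogenicity is secondary, the sample size was set for safety, no success criterion uses the GMRs, and the ANCOVA results will be reported in any case. The SAP also softens the ranking by calling the models first and second. All of that is true, and it limits the point to precision and clarity. It does not remove it, because the protocol assigns the main tables to the ANOVA and the SAP uses the ANOVA for the figures and for the contrast error term.

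The gain is also unknown, since saying that response is correlated with baseline supports no particular r. That stands. Below about r = 0.2 there is almost nothing to gain, and the 28% needs r = 0.7 without censoring. But the ANCOVA costs one degree of freedom, so its downside is under 1% in width.

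Fold rises are analysed too, which takes some account of baseline. An ANOVA of the fold rise is a cruder adjustment. With equal SDs its SD relative to the Day 29 ANOVA is √(2(1 − r)): 1.18 at r = 0.3, 1.00 at 0.5 and 0.77 at 0.7, always larger than √(1 − r²).

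With log10 baseline as covariate, the treatment contrasts for Day 29 titer and for fold rise are algebraically the same, apart from the different LLOQ rules in SAP 5.2. The GMR and GMFR comparisons in the forest plots would become nearly redundant. That is harmless.

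Finally, the contrast sentence has a coherent reading, with site-adjusted means and error both from the ANOVA, so it is ambiguous and not plainly wrong. Naming the ANOVA would also resolve it; the case for the ANCOVA rests on precision.

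**Conclusion.** The concern holds. The plan leads with the less efficient of its two models, against its own stated rationale and although the primary immunogenicity set guarantees a baseline result. The ANOVA is unbiased with near-nominal coverage, so no invalid conclusion follows from it; its intervals are wider than they need to be. Under the assumed SD of 0.6, the gain from leading with the ANCOVA is 2% to 28% of log-scale width for r from 0.2 to 0.7. With half of baselines below the LLOQ it is 3%, 10% and 22% at r = 0.3, 0.5 and 0.7. The width ratio depends on r and on the share below the LLOQ, and both will differ by serotype and assay. The contrast sentence needs repair whichever model leads. This change should be made, but it is not critical to the validity of the trial.

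**What to change.** Before unblinding:

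- In SAP 6.5.1, name the ANCOVA with log10 baseline as the lead model for the main tables and group contrasts, and keep the ANOVA as supportive.
- Rewrite the contrast sentence so that the means and the mean square error of each contrast come from one named model, the ANCOVA.
- In SAP 6.5.2, draw the bar plots and forest plots from the ANCOVA.
- In SAP 5.2, state which substituted value the baseline covariate takes when it is below the LLOQ.
- In SAP 6.1.3, limit the rule that drops baseline after non-convergence to the logistic model. A linear ANCOVA has a closed-form fit.
- Record the departure from Protocol 9.6.1 in SAP Section 7, which already lists one departure from the protocol.

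The cost is wording and one degree of freedom, with no new data. In the supportive Exposed Population, which does not require a baseline sample, subjects without a baseline result would drop out of the ANCOVA because missing data are not imputed. The supportive ANOVA would keep those who have a Day 29 result.

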9.6.2 Threshold analyses

For the 4 non-PCV20 serotypes that are in VAX-24, the % of subjects with a ≥ 4 -fold increase in OPA titer will be evaluated using a logistic regression model, with an indicator variable for achieving a ≥ 4 -fold increase in OPA titer as the dependent variable, and treatment group and study site as fixed effects and \log_{10} baseline titer as a covariate. The difference in proportions achieving a ≥ 4 -fold increase in OPA titer in each of the three VAX-24 dose levels group versus the PCV20 and the corresponding 95% CIs will be calculated. If the lower bound of the 95% CI is > 0.1 , the VAX-24 dose will be deemed statistically superior to PCV20.

The percentage of subjects achieving specified thresholds (eg, GMFR ≥ 4 in serotype-specific OPA and IgG, achieving OPA titer of at least serotype-specific LLOQ of the assay), and associated Wilson (score) 95% CI, will be calculated for the Day 29 visit data for each treatment group. A reverse cumulative distribution curve will be provided. Differences between pair-wise treatment groups may be determined via Fisher's exact tests.

10 ADDITIONAL INFORMATION

10.1 Ethical Conduct of the Study

The study will be performed in accordance with the protocol and consistent with International Conference on Harmonisation (ICH) GCP Guidelines and applicable local regulatory requirements and laws.

10.2 IRB Oversight

The study (protocol, informed consent form, recruiting materials, and any documents seen by the subject) will be reviewed and approved by an IRB appropriate to each study site. Subjects will not be recruited, consented, screened, or enrolled until the IRB has approved the required documentation. In addition, the IRB will review amendments to the protocol before their implementation.

The Investigator will retain all correspondence with the IRB in the trial master file.

10.3 Informed Consent

The Sponsor or designee will provide a master ICF template to each site for development of a site-specific ICF. At the Investigator's discretion, the site may develop a separate ICF for pre-screening as described in [Section 5.2](#).

All site-specific ICFs must be approved by the Sponsor or designee and the IRB and must comply with ICH GCP, local regulatory requirements, and legal requirements. The Sponsor or designee will advise the Site of required changes to the master ICF template during the study.

The Investigator will ensure that each potential study subject is fully informed about the nature and objectives of the study and possible risks associated with participation. Before informed consent is obtained, the Investigator, or a qualified person designated by the Investigator, will provide the potential study subject with ample time and opportunity to inquire about the details of the trial, and will answer all relevant questions to the potential study subject's satisfaction. The potential study subject will then decide whether to participate in the trial. The Investigator, or a qualified person designated by the Investigator, will obtain written informed consent from each study subject before any study-specific activity is performed.

The Investigator will retain the original and any amended signed and dated Informed Consent Form(s) at the study site and provide a copy to each study subject.

10.4 Subject Confidentiality

The Investigator will ensure that each subject's anonymity is maintained. In all documents submitted to the Sponsor and/or its designee, subjects can be identified by subject ID number and

initials. Documents not intended for submission to the Sponsor and/or its designee (eg, signed ICFs) must be maintained by the Investigator securely and must comply with all federal laws, regulations, and ICH GCP Guidelines.

10.5 Compensation for Injury

The Sponsor will adhere to local regulations and guidelines regarding clinical trial compensation to subjects whose health is adversely affected by taking part in the study. The applicable policy for compensation for injury will be described in the master ICF template.

10.6 Clinicaltrials.gov

For purposes of reporting to clinicaltrials.gov, the Sponsor is the responsible party and will provide information regarding this study in accordance with applicable regulations.

10.7 Public Disclosure and Publication Policy

All publication rights are delineated in the Clinical Study Agreement with the Investigator(s).

10.8 Amendments

The protocol may be amended only by the Sponsor.

The IRB must be informed of all amendments prior to implementation. In addition, the Investigator must obtain IRB approval for any amendments likely to affect the safety of study subjects prior to implementation.

The Sponsor may implement an amendment prior to IRB notification or approval only to eliminate an apparent, immediate hazard to study subjects. In that event, the Sponsor will notify the IRB in writing within 7 calendar days after the implementation.

Amendments, including descriptions and rationales, will be documented in this section of the protocol.

APPENDIX A: SCHEDULE OF EVENTS

	Study Visit:	Screening	Day 1 ^a	Day 8	Day 29	Month 3 and 6 (Phone)	Early Termination
	Window:						
Informed Consent	-30d	X		+3d	±3d	±5d	
Demographics, Medical History		X	X ^b				
Concomitant Medications		X	X	X	X ^d	X ^d	
Physical Exam(s), targeted		X	X ^b				
Vital Signs		X	X ^c				
Confirmation of Eligibility		X	X				
Serum for Immunogenicity			X ^b		X		
Randomization			X				
Study Vaccine Administration			X				
Post-vaccination Observation (at least 30 min)			X				
Issue Diary Instructions, Ruler, Thermometer; Conduct Training			X				
Review Diary Data				X			
AE Evaluation (Solicited and/or Unsolicited)			X	X	X	X ^d	

Refer to Section 6.2 for Procedures

Abbreviations: AE = adverse event; SAE = serious adverse event

- ^a Subjects may screen for up to 30 days prior to randomizing into the trial; a separate Screening visit may be conducted.
- ^b Conduct or collect prior to study vaccination (if indicated by updated medical history or change in health status, as applicable).
- ^c Vitals to be taken prior and after study vaccine administration (≥ 30 min).
- ^d New onset of chronic illnesses, SAEs, and associated concomitant medications collected after Day 29.
